### **Time to Symptomatic Progression**

Time to symptomatic progression will be measured as a 2-point increase in ECOG score, or the presence of constitutional symptoms, or the occurrence of pain in previously asymptomatic patient compared to baseline. ECOG performance status (Oken et al 1982) is used widely in cancer clinical trials to assess the progression of disease and how this affects patient's daily life (Appendix 1). ECOG performance status will be assessed at baseline and at each of the follow-up visits until study completion, with the exception of the 2-3 week post treatment visit when patients might still be experiencing post-embolization syndrome.

### **Time to Progression**

Time to progression (TTP) will include and be categorized as time to: local tumor progression (LTP), distant hepatic progression (DHP), and extra-hepatic progression (EHP). Local tumor progression (LTP) will be measured as the time from randomization until the first measurement of progression as determined by the central reading group using RECIST criteria as well as volumetric criteria for the target tumor. Local tumor progression (LTP) will be defined specifically as  $\geq 20\%$  increase from the smallest sum of measurements since the start of treatment (RECIST criteria, see above), or  $\geq 75\%$  increase in enhancing tumor volume. Distant hepatic progression (DHP) will be defined as the development of any new discontinuous disease within the liver, and the development of any extra-hepatic disease will constitute extra-hepatic progression (EHP).

### **Duration of Objective Response**

Duration of treatment response will be measured as the time from the date of first objective response until the first measurement of progression as determined by the central readers using the RECIST criteria.

### **Time to Treatment Failure**

Time to treatment failure (TTF) will be measured as the time from randomization until treatment discontinuation for any reason including, development of  $\leq 5\%$  necrosis, by volume, following the initial treatment or  $>50\%$  increase in sum of uni-dimensional measurements following later treatments, treatment toxicity, patient preference, or death.

### **Change in Alpha-fetoprotein**

Alpha-fetoprotein (AFP) will be measured at baseline, and then at each follow-up visit.

### **Time to Hospital Discharge**

Time to discharge will be measured as the time from the date of embolization until discharge for each embolization, and be reported as per embolization, not per patient.

### **Other Procedures or Interventions Required Secondary to Embolization**

Any additional procedures or interventions will be recorded in CRDB

### **Study Population**

Subjects for study will be recruited from MSKCC patient population, and will include patients with a diagnosis of HCC seen primarily by Hepatobiliary Surgery, GI Oncology, or GI Medicine. These patients may have had previous surgery, but will not have had previous radiation therapy, embolization or local-regional treatment of the current target tumor volume. Every effort will be made to recruit a diverse group of patients, including men and women of different ethnic backgrounds from the varied Memorial Sloan-Kettering referral population. The disease is more common in men and patients of Asian ethnicity. We plan to enter 100 patients into the study over a two-year period.

### **4.2 Intervention**

The intervention being studied is hepatic arterial embolization for the treatment of hepatocellular carcinoma using either a plain microscopic bead or the same bead loaded with doxorubicin. Baseline angiography including celiac and superior mesenteric angiography will be performed to delineate arterial anatomy, and blood supply to the tumor followed by catheter embolization.

### **Solitary HCC**

In the case of a solitary tumor, selective embolization will be performed. In the **Bead + Dox Arm** an attempt will be made to administer the entire 2-3 vial dose of 100-300 micron LC Bead containing a total of 150 mg of doxorubicin, followed by administration of unloaded microspheres (Bead Block) until stasis occurs. Whether the 150 mg of doxorubicin will be loaded in 2 or 3 vials (37.5 mg/ml or 25 mg/ml) will depend on the volume of tumor being treated. Patients in the **Bead arm** will be embolized beginning with 100-300 micron Bead Block and using larger size beads as necessary until stasis is evident.

## **Multifocal HCC**

In the case of multifocal bilobar disease or some large tumors with significant blood supply from both the right and left hepatic artery, either the right or left hepatic territory will be treated at the first session. This will be performed by placing the angiographic catheter selectively into either the right or left hepatic artery, and embolizing to stasis. In the **Bead + Dox Arm** 2-3 vials of 100-300 micron microspheres (LC Bead) will be prepared with 50 mg of doxorubicin/vial in an attempt to administer a total of 150 mg of doxorubicin. The goal will be to administer all 2 or 3 vials when possible and, if persistent antegrade flow is noted after the drug eluting beads have been used, then embolization will be continued using unloaded microspheres (Bead Block) until stasis occurs. Patients in the **Bead arm** will be embolized in a similar fashion using unloaded microspheres (Bead Block) only.

Patients requiring a second embolization to complete their treatment will undergo the second embolization within 2-6 weeks, depending on their recovery from the first session.

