#### Trial Arms

Patients will be randomized to one of two arms designated **Bead Arm** and **Bead + Dox Arm**, where the planned interventions are:

- **Bead Arm:** Hepatic arterial embolization with Bead Block microspheres, beginning with 100 – 300 micron beads, and using larger particles if necessary until stasis is evident.
- **Bead + Dox Arm:** Hepatic arterial embolization with 100-300 micron drug eluting microspheres (LC Bead) loaded with 150 mg Doxorubicin, followed by embolization with Bead Block microspheres (100-300 micron and larger size beads as necessary) until stasis is evident.

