### 5.3 LC Bead Doxorubicin Loading Instructions

LC Beads are suitable for loading doxorubicin-HC1 ONLY. Liposomal formulations of doxorubicin are not suitable for loading into LC Bead.

150 mg (2 vials, 75 mg each, or 3 vials, 50 mg each) doxorubicin HCL will be obtained from the pharmacy. Our pharmacy will load the doxorubicin

To obtain a final loading of 50mg doxorubicin per 2ml vial of LC Bead

- i. Reconstitute a vial containing 50mg of doxorubicin with 2ml of sterile water for injection. Mix well to obtain a clear solution (25mg/ml).
- ii. Remove as much saline as possible from a vial of using a syringe with a small gauge needle.
- iii. Using a syringe and needle add the 2ml of reconstituted doxorubicin solution directly to the vial of LC Bead.
- iv. Agitate the LC Bead/doxorubicin solution gently to encourage mixing, then allow to stand for the required time. At this point the LC Bead will be red and loaded to the extent stated. The solution usually will still have a red coloration,. For static loading the following times must be adhered to:

Product Cap Color	Nominal Size Range	Concentration of Doxorubicin Loading Solution	Minimum Time to achieve >90% Loading	Minimum Time to achieve 98% Loading
	100 $\mu$ -300 $\mu$	25mg/ml	30 minutes	60 minutes
	300 $\mu$ -500 $\mu$	25mg/ml	60 minutes	120 minutes

Although the solution retains a pink color, the majority of the doxorubicin will be loaded.

- v. Loading will take a minimum of 30 minutes for the smallest size LC Beads and up to 120 minutes for the largest size LC Bead.
- vi. Repeat above procedure with 2nd 50 mg vial of doxorubicin
- vii. Prior to use, transfer the LC Bead loaded with doxorubicin to a syringe and add an equal volume of non-ionic contrast media. Invert the syringe gently to obtain an even suspension of LC Bead.

Use the suspension of loaded LC Bead within 4 hours of addition of the contrast media. A pink coloration will be present in the suspension as approximately 0.3% (0.1mg) of the loaded drug elutes into the contrast media suspension.

- vii. A dose of up to 37.5mg doxorubicin per ml LC Bead can be loaded.
- viii. The maximum recommended total dose of doxorubicin per procedure is 150mg.

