**For 37.5mgs, the following loading times should be used:**

Product Cap Color	Nominal Size Range	Concentration of Doxorubicin Loading Solution	Minimum Time to achieve >90% Loading	Minimum Time to achieve 98% Loading
	100 $\mu$ -300 $\mu$	37.5mg/ml	30 minutes	60 minutes
	300 $\mu$ -500 $\mu$	37.5mg/ml	45 minutes	90 minutes

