### **Multifocal HCC**

In the case of multifocal bilobar disease, either the right or left hepatic territory will be treated at the first session. This will be performed by placing the angiographic catheter selectively into either the right or left hepatic artery, and embolizing to stasis. For patients receiving LC Bead, 2-3 vials of 100-300 micron LC Bead will be prepared. The goal will be to administer all vials when possible, and if persistent antegrade flow is noted after the drug eluting beads have been used, then embolization will be continued using 100-300 micron Bead Block until **stasis\*** occurs. When stasis is not evident after a total of 10 cc of microspheres (including the LC Bead) has been administered in this vessel, the next larger size of microspheres (300-500 micron) will be used. If stasis is not evident after 10 cc of 300-500 micron Bead Block has been given in that vessel, the next size (500-700 micron) particles will be used. In the event that sectoral or segmental branches of one side of the liver have to be catheterized selectively (for instance when there is an accessory vessel that arises separately, or when selective catheterization is necessary to avoid non-target embolization), after evaluation of the initial angiogram the LC Bead will be divided proportionally, and administered proportionally in each branch. After the entire dose of 100-300 micron LC Bead has been used, the vessels will be re-catheterized and embolized to **stasis\*** beginning with 100-300 micron Bead Block according to the method outlined above using up to 10 cc of each size microsphere in each vessel. Patients will never be treated with sizes other than 100-300 micron LC Bead.

Patients being treated with beads alone will have the vessels supplying one side of the liver catheterized as selectively as necessary, and embolized with 100-300 micron Bead Block, using up to 10 cc of 100-300 micron Bead Block in each vessel embolized. If **stasis\*** is not then evident, 10 cc of the next size particle will be used, and so on, as outlined above. This will be repeated in each vessel supplying tumor.

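### The multifocal preparation text and the numbered loading steps can each yield 100 mg of doxorubicin per session against the stated 150 mg; separately, an early two-session re-treatment cannot be completed under the annual limit

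*Combined protocol and SAP*

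**What the plan says.** Section 4.1 (Trial Arms) defines the Bead + Dox arm by "drug eluting microspheres (LC Bead) loaded with 150 mg Doxorubicin". The same total stands in sections 1.0 and 5.0, in both parts of 4.2, in the opening of 5.3 and in 9.0 (Solitary HCC).

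The make-up of that total is described as follows:

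- **4.2, Solitary HCC:** "Whether the 150 mg of doxorubicin will be loaded in 2 or 3 vials (37.5 mg/ml or 25 mg/ml" is left to depend on tumor volume.
- **4.2, Multifocal HCC:** two or three vials "will be prepared with 50 mg of doxorubicin/vial in an attempt to administer a total of 150 mg of doxorubicin". The goal is to give all of them when possible.
- **5.3, opening:** "150 mg (2 vials, 75 mg each, or 3 vials, 50 mg each) doxorubicin HCL will be obtained from the pharmacy". The pharmacy does the loading.
- **5.3, numbered steps:** headed "To obtain a final loading of 50mg doxorubicin per 2ml vial of LC Bead". Step vi repeats them for a second "50 mg vial of doxorubicin". There is no step for a third.
- **5.3, after the steps:** loading up to 37.5 mg/ml is allowed, and a table headed "For 37.5mgs, the following loading times should be used" gives times but no separate steps.
- **9.0, Multifocal HCC:** "2-3 vials of 100-300 micron LC Bead will be prepared", with neither mg per vial nor a total.

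On re-treatment, section 9.0 defines one treatment of multifocal bilobar disease as two sessions and puts a two-session treatment at 300 mg. Section 10.0 calls for re-treatment in the same arm by an identical embolization protocol. Footnote 7 of the section 10.0 schedule limits doxorubicin to 450 mg per annum, and the 11-12 month text limits LC Bead to three embolizations within one year. For the CTs from 5-6 months on, footnote 7 gives a re-treatment window of two months, plus or minus two weeks. The visit texts give six weeks.

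**The concern.** Doxorubicin is the element that separates the two arms, and the arm is defined by its amount. If one preparation text leads to 100 mg and another to 150 mg, patients in the same arm could have different amounts prepared according to which text was followed. The multifocal text governs the patients who commonly have two sessions, so any difference would double before the 2-3 week CT that supplies the primary endpoint. The instruction in section 9.0 to record the amount given when stasis comes early stands in the solitary-tumor text and is not repeated in the multifocal text.

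The annual limit raises a separate question: whether a patient already given two LC Bead sessions can receive a full two-session re-treatment in the same year. This arises after the response CT, so it bears on later follow-up and not on the primary endpoint.

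**Working it through.** **1. Vials.** Inputs: 2 ml of LC Bead per vial (section 5.2), and the vial counts and contents listed above. Prepared dose = vials × mg per vial, or vials × 2 ml × mg/ml.

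The plan's own figure reproduces by two routes:

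- 2 vials × 2 ml × 37.5 mg/ml = 2 × 75 = 150 mg
- 3 vials × 2 ml × 25 mg/ml = 3 × 50 = 150 mg

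The two texts in question give:

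| Text | Calculation | Prepared |
|---|---|---|
| 4.2 Multifocal, three vials | 3 × 50 | 150 mg |
| 4.2 Multifocal, two vials | 2 × 50 | 100 mg |
| 5.3, steps i-vi | 50 + 50 | 100 mg |

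The difference is 150 − 100 = 50 mg, and 50/150 = 33%. Over a two-session treatment it is 2 × 100 = 200 mg against 2 × 150 = 300 mg, the figure in section 9.0.

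**2. Annual limit.** 450/150 = 3 sessions, so the mg limit and the session limit agree with each other. For a first treatment plus one re-treatment:

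| Sessions | Total | Nominal dose |
|---|---|---|
| 1 + 1 | 2 | 300 mg |
| 1 + 2 or 2 + 1 | 3 | 450 mg |
| 2 + 2 | 4 | 600 mg |

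Only 2 + 2 exceeds the limit. Four sessions would meet the mg limit if they averaged 450/4 = 112.5 mg or less, but the limit of three embolizations would still exclude the fourth.

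**3. When the fourth session falls.** Weeks are counted from the first session. The sum is: gap between first and second session (2-6) + time from Time 0 to the CT + wait for re-treatment (0-6 under the visit texts) + gap to its second session (2-6). Assumptions: the year runs from the first session, one month is 4.35 weeks, and the earliest case re-treats on the scan date.

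| CT that triggers re-treatment | Earliest | Latest |
|---|---|---|
| 10-14 weeks | 2 + 10 + 0 + 2 = 14 | 6 + 14 + 6 + 6 = 32 |
| 5-6 months | 2 + 21.7 + 0 + 2 = 25.7 | 6 + 26.1 + 6 + 6 = 44.1 |
| 8-9 months | 2 + 34.8 + 0 + 2 = 38.8 | 6 + 39.1 + 6 + 6 = 57.1 |
| 11-12 months | 2 + 47.8 + 0 + 2 = 51.8 | 6 + 52.2 + 6 + 6 = 70.2 |

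With footnote 7's longer wait (8.7 + 2 = 10.7 weeks), the latest 5-6 month case is 6 + 26.1 + 10.7 + 6 = 48.8 weeks. The first two rows therefore always lie inside 52 weeks. The last two may lie beyond.

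**4. Re-treatment window.** Read as a target, footnote 7 gives 8.7 ± 2 = 6.7 to 10.7 weeks (6 to 10 if two months means eight weeks), which meets the six-week rule at week 6 at most. Read as an upper bound, re-treatment within six weeks satisfies both.

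**The case against.** The best answer on the vials is that the total is never in doubt. It is stated many times, including in the sentence that mentions 50 mg vials. The opening of 5.3 sets out both routes to 150 mg and says that the pharmacy loads the drug. Section 9.0 restates 150 mg per session for two-session patients, although it uses the word treatment for a session there. To prepare only 100 mg, staff would have to pass over all of this. That stands, and it limits the point to disagreement between passages. A reader might infer that the plan offers no route to 150 mg, or that patients received 100 mg; the documents support neither. The disagreement remains, because the multifocal text allows two vials at 50 mg and the only stepwise instructions end at the second such vial.

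It is also fair that 150 mg is an aim. Section 4.2 speaks of an attempt, and section 9.0 provides for early stasis in solitary tumors. So 100 against 150 mg is a difference in what is prepared, and the amount delivered may be lower under either text.

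On re-treatment, a reader might infer that the plan permits 600 mg in a year. It does not: the limit is unconditional and can be read as overriding. Nor does every 2 + 2 sequence collide with it, as the later CTs show. The word identical describes the embolization protocol and does not fix the number of sessions, which depends on tumor burden at the time. What remains is a gap: no passage says how a re-treatment cut short by the limit is handled, or when the year starts.

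**Conclusion.** The vial point holds and is the main one. Section 4.2 (Multifocal HCC) with two vials, and the numbered steps of 5.3, each prepare 100 mg per session where the plan states 150 mg: 50 mg or 33% less, and 200 against 300 mg over two sessions. With three 50 mg or two 75 mg vials there is no difference. A reader might infer a biased response rate in the Bead + Dox arm. The documents do not support that, since they give neither the number of patients affected nor any relation between dose and response.

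The annual-limit point holds in a narrower form. It is certain only for a two-session first treatment followed by a two-session re-treatment triggered by the 10-14 week or 5-6 month CT, with the fourth session at about weeks 14-32 or 26-49. This assumes a year counted from the first session. How many patients would follow that path is not given, and any effect on time to progression or survival cannot be derived.

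The two re-treatment windows are a minor mismatch.

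**What to change.** The sponsor should reconcile section 4.2 (Multifocal HCC) and the numbered steps of 5.3 with section 4.2 (Solitary HCC) and the opening of 5.3, so that vial count, mg per vial and total agree wherever they appear.

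The same amendment should reconcile the re-treatment texts of section 10.0 with footnote 7 and the annual limit. It should say when the year starts and how a re-treatment that the limit leaves incomplete is handled, and give one re-treatment window for each CT.

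Which dose, limit or timing is right is for the sponsor to settle; none is proposed here. The cost is one clarifying amendment, with no extra patients, visits or procedures.

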## **5.0 THERAPEUTIC/DIAGNOSTIC AGENTS**

- **Bead Arm:** Hepatic arterial embolization with Bead Block microspheres, beginning with 100-300 micron spheres, and using larger sizes as outlined above until stasis is evident.
- **Bead + Dox Arm:** Hepatic arterial embolization with 100-300 micron drug eluting microspheres (LC Bead) loaded with 150 mg Doxorubicin, followed by embolization with Bead Block microspheres until stasis.

### **5.1 Bead Block Product Description**

Bead Block comprises a range of sizes of hydrophilic microspheres produced from polyvinyl alcohol (PVA) and supplied in sterile pre-filled syringes containing 1 ml or 2 ml of microspheres in sterile saline. These are intended for single use, should be stored in a cool, dry and dark place, and used by the date indicated on the syringe label. They are FDA approved for use in the embolization of hypervascular tumors and arteriovenous malformations. These microspheres, like all agents used for arterial embolization, are mixed with radiographic contrast prior to administration in order to allow for fluoroscopic control of the embolization procedure.

### **5.2 LC Bead Product Description**

Bio-compatible LC Bead (a.k.a. DC Bead in Asia & Europe) microspheres are preformed soft, deformable microspheres that may be loaded with doxorubicin and used to occlude blood flow to a cancerous tumor. LC Bead microspheres consist of a macromere derived from PVA. The fully polymerized microsphere is approximately 90% water and is compressible to approximately 30% by diameter. The microspheres can be delivered through conventional catheters (4-5Fr) or micro-catheters in the 2-3Fr range. These microspheres, like all agents used for arterial embolization, are mixed with radiographic contrast prior to administration in order to allow for fluoroscopic control of the embolization procedure.

LC Bead microspheres are supplied in glass vials containing 2ml of microspheres in 6ml of saline that do not require special handling, and should be stored in a cool, dry, dark place in original vial. The product is sterilized by steam.

**Loading Prior to Use:** LC Bead may be loaded with Doxorubicin immediately prior to use or by storing the vial with loading solution in a fridge (2-8°C) overnight prior to the procedure.

The recommended loading dose is 25mg Doxorubicin per 1ml of LC Bead. The maximum loading dose is 37.5mg Doxorubicin per 1 ml of LC Bead. The recommended total dose of Doxorubicin combined with LC Bead per procedure is 150mg.

Contrast can be added to the LC Bead /Doxorubicin mix immediately prior to use without affecting the Doxorubicin loading or the stability of the loaded drug. After mixing with contrast, the LC Bead Doxorubicin solution is stable for up to 8 hours at ambient temperature. In order to obtain a homogenous suspension of Doxorubicin loaded LC Bead an equivalent volume of non-ionic contrast media should be added to the loaded LC Bead mixture.

**Disposal of Unused DC Bead:** Unused LC Bead should be disposed of as cytotoxic clinical waste.

### 5.3 LC Bead Doxorubicin Loading Instructions

LC Beads are suitable for loading doxorubicin-HC1 ONLY. Liposomal formulations of doxorubicin are not suitable for loading into LC Bead.

150 mg (2 vials, 75 mg each, or 3 vials, 50 mg each) doxorubicin HCL will be obtained from the pharmacy. Our pharmacy will load the doxorubicin

To obtain a final loading of 50mg doxorubicin per 2ml vial of LC Bead

- i. Reconstitute a vial containing 50mg of doxorubicin with 2ml of sterile water for injection. Mix well to obtain a clear solution (25mg/ml).
- ii. Remove as much saline as possible from a vial of using a syringe with a small gauge needle.
- iii. Using a syringe and needle add the 2ml of reconstituted doxorubicin solution directly to the vial of LC Bead.
- iv. Agitate the LC Bead/doxorubicin solution gently to encourage mixing, then allow to stand for the required time. At this point the LC Bead will be red and loaded to the extent stated. The solution usually will still have a red coloration,. For static loading the following times must be adhered to:

Product Cap Color	Nominal Size Range	Concentration of Doxorubicin Loading Solution	Minimum Time to achieve >90% Loading	Minimum Time to achieve 98% Loading
	100 $\mu$ -300 $\mu$	25mg/ml	30 minutes	60 minutes
	300 $\mu$ -500 $\mu$	25mg/ml	60 minutes	120 minutes

Although the solution retains a pink color, the majority of the doxorubicin will be loaded.

- v. Loading will take a minimum of 30 minutes for the smallest size LC Beads and up to 120 minutes for the largest size LC Bead.
- vi. Repeat above procedure with 2nd 50 mg vial of doxorubicin
- vii. Prior to use, transfer the LC Bead loaded with doxorubicin to a syringe and add an equal volume of non-ionic contrast media. Invert the syringe gently to obtain an even suspension of LC Bead.

Use the suspension of loaded LC Bead within 4 hours of addition of the contrast media. A pink coloration will be present in the suspension as approximately 0.3% (0.1mg) of the loaded drug elutes into the contrast media suspension.

- vii. A dose of up to 37.5mg doxorubicin per ml LC Bead can be loaded.
- viii. The maximum recommended total dose of doxorubicin per procedure is 150mg.

